**VII. SENSITIVITY ANALYSES**

The following eight sensitivity analyses (SA1-SA8) in *Table 5* below were determined *a priori*. Additional sensitivity analyses may be considered *post hoc* upon review of preliminary results with the FDA RCA team. Unless otherwise specified, all sensitivity analyses will be applied in response to the primary objective but not the secondary objectives.

*Table 5: Summary of all sensitivity analyses planned a priori*

Category	Brief Description	Detail / Purpose
Inclusion/exclusion criteria (more specific)	SA1: Restrict study population to hospitalizations occurring after release of initial RECOVERY findings*	
Detail: Restrict cohort entry to on or after June 16, 2020, given the release of the RECOVERY results in early June 2020.
 
Purpose: Evaluate whether there is (qualitative) heterogeneity of the HR (which may be due to treatment pattern changes) after the substantial increase in DEX use in the US.

	SA2: Restrict study population to patients with immediate treatment initiation*	
Detail: Restrict DEX treatment index to DEX initiation on, or within 1d after, admission date.
 
Purpose: Evaluate whether there is (qualitative) heterogeneity of the HR (which may be due to covariate differences in patients treated earlier vs. later in the hospital stay) when restricting to DEX use upon admission, noting that the 1 day after admission was added to account for patients who may be admitted late in the evening who do not initiate treatment until the next morning.

Inclusion/exclusion criteria (more sensitive)	SA3: Broaden population to include patients with less frequent medical encounters*	
Detail: Lengthen baseline window to lookback 365 days to allow for better capture of covariates among patients who do not have as frequent medical encounters (office visit or otherwise). Evaluate whether covariate status using 183 day versus 365 day lookback is differential by treatment.
 
Purpose: Evaluate whether HR is robust within a broader cohort that may include people with less healthcare utilization (patients without a healthcare encounter within 183 days that do have one within 365 days prior to admission) prior to hospitalization for COVID-19. Determine if the lookback period impacts the distribution of baseline characteristics.

	SA4: Broaden patient population to include patients with confirmed COVID after treatment index*	
Detail: Additionally include patients with positive or presumed positive lab values or COVID-19 diagnosis occurring anytime during hospitalization, including discharge diagnoses.
 
Purpose: Evaluate whether HR is robust within a broader cohort including people without a COVID-19 diagnosis prior to or at admission. Will increase the sample size by approximately 10%, but may have the potential for misclassification of patients who were hospitalized for reasons other than COVID-19 who had a secondary diagnosis of COVID-19 or contracted COVID-19 during hospitalization as patients hospitalized for COVID-19.

Category	Brief Description	Detail / Purpose
Follow up censoring	SA5: Broaden the follow-up period for capturing inpatient mortality endpoints*	
Detail: Determine whether treatment with DEX reduces the risk of inpatient mortality within 60 days during the initial hospitalization.
 
Purpose: Evaluate effect of DEX on risk of inpatient death over a longer time frame. Aligns with mortality endpoint definition used in dexamethasone-ARDS trial [Villar 2020].

Additional subgroup	SA6: Stratify by ICU at Treatment index	
Detail: Estimate HR within ICU subgroup, defined based on the presence of a medical encounter with a revenue or department code indicating ICU at treatment index.
 
Purpose: Evaluate whether patients who initiate treatment while in the ICU differ from those who do not (within the overall cohort), an alternative proxy for COVID-19 severity.

Alternative subgroup definition	SA7: Define COVID-19 severity based on procedures alone	
Detail: Estimate HR within each of the mWHO subgroups using an algorithm that relies on procedural encounters only for defining O2/NIV and IMV (without the additional diagnostic encounters included in the primary definitions).
 
Purpose: Evaluate the impact of the robustness of findings among patients identified as O2/NIV and IMV and those identified as having neither (no O2) and understand the impact of the shift from lower to higher COVID-19 severity on the effect of DEX+ on 28-day mortality.

Inclusion/exclusion criteria related to RECOVERY	SA8: One comprehensive sensitivity analysis that attempts to more closely resemble RECOVERY population	
Detail:
 
 
1. Remove new user washout
 
2. Exclude patients aged 80 years or older
 
3. Exclude patients with systemic fungal infections
 
 
Purpose: To more closely align with RECOVERY design and baseline population
 
 
1. RECOVERY included any use of DEX.
 
2. Our study population has half the number of patients 80+ as RECOVERY due to under-report of older patients in our commercial data source, and these patients may therefore be selectively different.
 
3. RECOVERY trial excluded patients contraindicated “in the opinion of the attending clinician.” Systemic fungal infection is the only contraindication listed in the package insert for DEX, so excluding these patients is an attempt to satisfy this criterion.
 

\* Alternative versions of the study diagrams for these sensitivity analyses are illustrated in Appendix B.

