## **B. Randomized Evaluation of COVID-19 Therapy (RECOVERY): Efficacy of dexamethasone**

The RECOVERY trial, which first reported preliminary results on June 22, 2020, was an open-label, 1:2 randomized controlled trial of 6,425 patients randomized to either 6 mg of DEX daily for 10 days (n = 2,104) or usual care (n = 4,321). Overall, 22.9% of patients assigned to the DEX group died within 28 days of randomization vs. 25.7% of the control arm (rate ratio [RR] of 0.83, 95% CI [0.75, 0.93]). The difference in survival between the two groups varied noticeably when stratified by baseline COVID-19 severity level. While the incidence of death was lower in the DEX group, compared to the usual care group, among patients receiving IMV (RR: 0.64, 95% CI [0.51, 0.81]) and among those receiving supplemental O2 therapy but not IMV (RR: 0.82, 95% CI [0.72, 0.94]), there was no discernable difference among patients who were not receiving any supplemental O2 (RR: 1.19, 95% CI [0.91 to 1.55]) [*RECOVERY 2020*].

The effectiveness of DEX in preventing death among moderate to severe COVID-19 patients has not yet been confirmed or established in routine care, yet DEX utilization has substantially increased in the US since June 2020 [*Action 2021*]. Thus, to evaluate the effectiveness of DEX in preventing death under routine use in a timely manner, we sought to conduct an observational cohort study using US-based real-world data (RWD).

[figure not shown]
In one of the explorations conducted prior to the finalization of this protocol [see *Appendix A.2. Exploration 2*], we compared the distribution of key patient characteristics between a version of our hospitalized US-based RWD study cohort to those reported for the hospitalized UK-based patients randomized in the RECOVERY trial. The RECOVERY trial was a large, pragmatic randomized trial that simplified the data collection process in an effort to minimize the already heavy burden of the pandemic on frontline workers. Exploration of baseline clinical differences between the real-world study and trial populations was therefore limited by the degree of available information for the trial patients. However, among the available RECOVERY trial data, we identified important clinical and demographic differences in the trial population versus this study's populations at baseline.

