### 2. Treatment index

#### **Primary Objective -- New users of DEX (DEX+) versus matched non-users of CSI (CSI-):**

From the patients who enter the cohort, new users of DEX between the admission date (*Day 0*) and 1 day prior to discharge date (*Day D-1*) or a maximum period of 21 days after admission (*Day 21*) will be selected. Greater than 80% of the patients who initiated DEX did so within 1 or 2 days of their hospitalization. A sensitivity analysis (SA2) will be conducted to explore initiation dates further. For each new user of DEX, at least 1 patient who has not (yet) used any CSI as of the DEX patient's index date or within the 90-day washout period prior matched on the

criteria defined in Table 2 below will be randomly risk-set sampled (RSS). DEX+ versus CSI-matching ratios of 1:1, 1:2, 1:3, and 1:4 will be considered to select up to 4 non-user referent patients for each exposed, and the ideal ratio will be selected based on the diagnostic criteria [defined below in section *VI.B. Diagnostic phase and checklist*].

RSS matching allows us to proxy the ‘standard of care’ by randomly selecting 1 or more patients who have not initiated DEX from the risk set of patients who are eligible for initiating DEX at the same time [*Li 2001*]. Since the COVID-19 pandemic and treatment of patients with COVID-19 is rapidly changing over time, there is much potential for calendar-time bias. Furthermore, patients prescribed DEX may appreciably differ from those not prescribed DEX. Employing an RSS that matches DEX users and non-users on the date of DEX treatment (in the users) and time since admission will minimize the potential for this bias. Cohort entry month will also be included in the propensity score (PS) calculation to further adjust for time-related biases. Geographic region was considered for the RSS matching criteria. However, during our data explorations, the comparison of baseline balance showed that matching without region yielded better baseline balance than matching with region. Therefore, we removed region from the RSS matching. However, given known regional differences, we still account for region in our propensity score model.

The *treatment index date* (Day T) for patients who are users and for the matched non-user referent patients will be defined by the index date of the matched users.

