**B. APPENDIX B: Study design diagrams for each sensitivity analysis**

**SA1: Restrict study population to hospitalizations occurring after release of initial RECOVERY findings**

Detail: Restrict cohort entry to on or after June 16 given the release of the RECOVERY results in early June.

Purpose: Evaluate whether there is (qualitative) heterogeneity of the HR, which may be due to treatment pattern changes, after the substantial increase in DEX use in the US.

Figure B.1. Study diagram (SA1)

[figure not shown]

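### SA1 and SA2 state a heterogeneity purpose but estimate the HR in one stratum only, so any difference by era or by timing of DEX start is seen diluted against an overlapping primary HR.

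*Protocol*

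**What the plan says.** Both analyses sit in Table 5 under more specific inclusion and exclusion criteria, and section V.C.3 describes them as further exclusions.

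- **SA1.** The detail line reads "Restrict cohort entry to on or after June 16, 2020, given the release of the RECOVERY results in early June 2020". The purpose is to evaluate heterogeneity of the HR, "which may be due to treatment pattern changes) after the substantial increase in DEX use in the US".
- **SA2.** The detail line reads "Restrict DEX treatment index to DEX initiation on, or within 1d after, admission date". The purpose is again worded as heterogeneity, with this explanation: "which may be due to covariate differences in patients treated earlier vs. later in the hospital stay) when restricting to DEX use upon admission". Section V.C.2 adds that SA2 will look further into initiation dates, and says of those dates: "Greater than 80% of the patients who initiated DEX did so within 1 or 2 days of their hospitalization".

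Appendix B repeats both restrictions. The protocol plans no HR for entry from 1 April to 15 June 2020, no HR for DEX starts after Day 1, no interaction term and no ratio of HRs. SA3 and SA4, by contrast, ask only whether the HR is robust, and section V.D names both strata for ICU status (SA6).

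On the date, section II.B says of the RECOVERY trial "which first reported preliminary results on June 22, 2020", and section II.A gives the same publication date.

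**The concern.** Whether an HR differs between eras, or between early and late starters, is a question about two strata. SA1 and SA2 each estimate one. The only available comparator is the primary HR, which is itself partly made up of the restricted cohort, so the two estimates are pulled together by construction.

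If the subset carries most of the events, a small shift between restricted and primary HR is compatible with no heterogeneity and also with a substantial difference, including a change of direction, in the patients left out. The likely report would be that the HR was robust, under a stated purpose of having looked for heterogeneity.

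The SA1 cut raises a smaller matter. If the first report was on 22 June, patients entering on 16 to 21 June entered before release, although SA1 is titled as covering hospitalizations after release.

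**Working it through.** The protocol gives no sample size, event count or power for SA1 or SA2, so there is no figure to reproduce. What follows is an illustration with its assumptions stated.

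**Inputs from the protocol.** Table 4, item 1: 80% power, two-sided 0.05, HR 0.8. Section V.C: first entry 1 April 2020, last entry 60 days before the end of data. Section IV: last data date 22 February 2021 in the March 2021 cut.

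**Assumed.** 1:1 matching (the protocol allows up to 1:4), the minimum event count, and the share f of events in the subset.

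**Events.** 4 × (1.96 + 0.8416)² / (ln 0.8)² = 630.5, so 631.

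**Dilution.** To a good approximation, log HR(primary) = f × log HR(subset) + (1 − f) × log HR(complement). Hence HR(subset)/HR(primary) = [HR(subset)/HR(complement)]^(1−f). For a true subset-to-complement ratio of 0.75:

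| Assumed f | Ratio visible against the primary HR |
|---|---|
| 0.25 | 0.75^0.75 = 0.806 |
| 0.50 | 0.75^0.50 = 0.866 |
| 0.80 | 0.75^0.20 = 0.944 |
| 0.90 | 0.75^0.10 = 0.972 |

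**Fixed primary HR of 0.80, f = 0.80.** The subset has about 505 events and the complement about 126; SE = 2/√events.

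- Complement HR 1.00: log HR(subset) = ln 0.80 / 0.80 = −0.279, HR 0.757 (95% CI 0.64 to 0.90). The shift seen is 0.80 to 0.757.
- Complement HR 1.19 (illustrative): log HR(subset) = (−0.223 − 0.2 × 0.174)/0.8 = −0.322, HR 0.724 (0.61 to 0.86). That interval still contains 0.80.

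**A reversal, f = 0.80.** With early HR 0.80 and late HR 1.25, the primary HR is exp(0.8 × ln 0.80 + 0.2 × ln 1.25) = 0.87 (0.75 to 1.02) and SA2 gives 0.80 (0.67 to 0.95). The late-start HR of 1.25 (0.88 to 1.77) would not be reported.

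**What is known about f.**

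- *SA2.* The figure of more than 80% covers starts within 1 or 2 days, whereas SA2 takes Day 0 and Day 1 only, and it counts starters rather than deaths. In Table A.2 (an earlier exploratory cohort, for the DEX− comparison) the DEX+ median time since hospitalization is 2 [2, 3] days. If admission is Day 0, about 25% or fewer start by Day 1; if admission counts as day 1, at least 50% do.
- *SA1.* 1 April to 15 June is 76 of the 268 entry days to 24 December 2020, or 28%. The share of DEX starters in that period is probably smaller, since section II.B says use rose substantially since June 2020.

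**What estimating the complement would give.** At f = 0.80 and complement HR 1.00, the complement CI is about 0.71 to 1.42. The contrast has z = 0.279 / √(4/504.8 + 4/126.2) = 0.279/0.199 = 1.40, and power Φ(1.40 − 1.96), about 29%. With complement HR 1.19, power is about 70%. At f = 0.90 and complement HR 1.00 it is about 15%.

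**The case against.** The strongest reply is that these are ordinary restriction analyses. They are filed as tighter eligibility criteria, earlier versus later treatment appears only in a parenthesis as a possible cause, and the bracketed word qualitative may mean no more than an informal look against the primary HR. SA1 also has a second role in section VIII.A, checking how ARDS is reported after the early months. Formal contrasts are commonly left to an SAP, and Table 5 allows post hoc analyses. At the minimum sample size the contrast would be weak anyway.

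Much of this limits the point. A reader might infer that SA1 and SA2 cannot answer their question at all. The documents do not support that: with strictly nested samples the z for subset against primary equals the z for subset against complement (1.40 in both at f = 0.80, complement HR 1.00), and the complement could be roughly back-calculated. Table 2's first time-since-admission category, 0 to 1 days, matches SA2's window, so the risk sets nest at that stage. However, the protocol does not plan the back-calculation, and it does not say whether matching and the propensity score are redone, which could break the nesting.

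A reader might also take 80% as SA2's share of events. It is not given, and Table A.2 allows much less. In the reversal example the primary HR would be 1.12 at f = 0.25, 1.00 at f = 0.50 and 0.89 at f = 0.75, against 0.80 in SA2, so the contrast is plain at the lower shares.

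Nor do the documents show that the pre-June era is the more informative one. Section VIII.A warns of poorer ARDS capture and incomplete uptake of the U07.1 code early on.

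What stands is that the purpose is worded as heterogeneity, the table fixes a single-stratum estimate, and an unspecified post hoc option is not a planned remedy.

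**Conclusion.** The point holds in limited form. SA1 and SA2 as written check robustness in a restricted cohort; they meet their stated heterogeneity purpose only indirectly, through a contrast reduced to the power 1 − f. The size depends on f, which the protocol does not give: a true HR ratio of 0.75 would appear as anything from about 0.81 (f = 0.25) to 0.97 (f = 0.90), and as about 0.94 at f = 0.80. These figures also assume approximate pooling of log HRs by events; the intervals and power add 1:1 matching and 631 events. A reversed effect in late starters or early-era entrants would never be displayed directly at any f. The primary estimate is not affected.

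The date conflict is real but minor. It concerns six entry days, and some of those patients could be indexed after 22 June because treatment index may fall up to Day 21. A reader might infer that 16 June is the wrong cut; the documents show only that the dates disagree.

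**What to change.** For SA1 and SA2, report the HR in both strata: entry before and on or after the SA1 cut date, and DEX start on Day 0 to 1 and after Day 1. Add the ratio of the two HRs with its 95% CI, and state whether matching and the propensity score are redone within strata. Present the results as estimation, as section VI.C already does for subgroups below the minimum sample size. If the sponsor does not want this, reword both purposes as robustness in a restricted cohort.

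Separately, reconcile the early June release and 16 June cut in SA1 (Table 5, section VIII.A and Appendix B) with the 22 June 2020 date in sections II.A and II.B.

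The cost is two further stratum estimates and two ratios from patients already in the cohort. The drawback is imprecision: under the assumptions above (f = 0.80, complement HR 1.00, 631 events), the complement interval runs from about 0.71 to 1.42 and the contrast has about 29% power, so a wide ratio must not be read as evidence of homogeneity.

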### 3. Exclusion criteria

Patients who meet any of the following criteria will be excluded from the study cohort:

- No interaction with the healthcare system (medical encounter) in the 183 days prior to and including hospital admission (*Day -183 to Day 0*) to minimize the potential for misclassification of baseline covariates and/or new use
- No age or sex recorded in the 183 days prior to and including hospital admission (*Day -183 to Day 0*) as required for matching
- No geographic region recorded in 183 days prior to and including hospital admission (*Day -183 to Day 0*) as necessary to adjust for regional variation
- Any recorded use of any CSI (dispensing or remaining supply) in the 90-day washout prior to the treatment index date (*Day T-90 to Day T-1*) to satisfy new use definition
- Any record of a COVID-19 vaccine recorded on or any time prior to the treatment index date given that these patients are assumed to be selectively different (*Day S to Day T*)

The following will be evaluated (one at a time) in sensitivity analyses in order to tighten or loosen some of the exclusion criteria:

- Two sensitivity analyses will restrict the study population by adding the following further exclusions: (1) patients who entered the cohort prior to the release of the initial RECOVERY trial results; and (2) patients who initiated DEX use more than 1 day after the hospital admission date [see section *VII. SENSITIVITY ANALYSES, SA1, SA2*].
- Two sensitivity analyses will broaden the study population by loosening exclusions: (1) extend the lookback period to confirm a prior healthcare encounter to 365 days to allow for better capture of covariates among patients who do not have as frequent medical encounters (office visit or otherwise); and (2) allow patients with confirmed COVID-19 only after treatment index during the index hospitalization (no confirmation on/prior to treatment index or within 21 days prior to admission) [see section *VII. SENSITIVITY ANALYSES, SA3, SA4*].

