- **COVID-19 diagnosis:** The unique ICD-10 code for COVID-19 diagnosis (U07.1: COVID-19, virus identified) was created by the World Health Organization (WHO) in April 2020. Prior to the widespread use of the new code, other respiratory-related codes were used for billing purposes. We chose to delay the start of our cohort selection to April when the code was available. There is a possibility that early on, some facilities were not yet using the new code. However, given our findings from exploration 1 [see *Appendix A.1. Exploration 1*], concerns about the specificity of the ICD-10 codes other than the designated U07.1 code, we agreed to proceed with the definition of confirmed COVID-19 via diagnosis of U07.1 or positive/presumptive positive SARS-CoV-2 diagnostic laboratory test result.
- **Unstructured laboratory encounter data:** In addition to using the unique diagnosis code for COVID-19 (ICD-10: U07.1), we will include patients without a diagnosis claim if they have laboratory results identifying positive or presumed positive SARS-CoV-2 diagnostic test via nucleic acid amplification test (NAAT). The laboratory data has unstructured free-text for test type and results, which present a challenge. Although we anticipate that we will not be able to categorize all COVID-19 laboratory results, we rely on an algorithm developed by the data vendor to discern the majority of test types and results.

- **Open claims:** Data from open claims can be captured within days of a healthcare encounter to provide near-real-time data. However, the composition and completeness may be less stable for the most recent calendar dates. Based on our findings from exploration 5, we have truncated cohort entry to remove the last 60 days, which should minimize this concern [see *Appendix A.5 Exploration 5*].
- **Lack of enrollment information in open claims to determine denominator of patients at risk with the same potential to contribute baseline data:** Without beneficiary enrollment information like that included with closed claims data, use of “open” datasets limits the ability to clearly determine when a patient is observable or “at risk.” However, we are confident that our cohort will include all patients hospitalized available in the data and will additionally require the presence of any encounter during the 183-day baseline period for inclusion as a proxy for enrollment and extend this period to 365 days in a sensitivity analysis.

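### SA3 is cited as part of the answer to missing enrollment data, but it loosens the encounter proxy and lengthens the covariate window together, so its hazard ratio cannot show whether poor observability biases the primary result

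*Protocol*

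**What the plan says.** Protocol VIII.A (Addressed in Design and Analyses) has an entry on the lack of enrollment information. It notes that open claims come "Without beneficiary enrollment information like that included with closed claims data" and that this "limits the ability to clearly determine when a patient is observable" or at risk. The remedy is to require an encounter in the 183-day baseline "as a proxy for enrollment and extend this period to 365 days in a sensitivity analysis". That analysis is SA3.

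Section V.C.3 places SA3 among those that relax the entry criteria: "Two sensitivity analyses will broaden the study population by loosening exclusions".

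Section VII, Table 5, gives the detail: "Lengthen baseline window to lookback 365 days to allow for better capture of covariates". The broader cohort may include "patients without a healthcare encounter within 183 days that do have one within 365 days prior to admission". SA3 also plans to check whether covariate status under the two lookbacks differs by treatment, and whether the lookback changes the baseline distributions. Appendix B repeats this.

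Section IV states that the database holds both open and closed medical claims. None of SA1 to SA8 restricts to patients with closed-claims enrollment or otherwise tightens the encounter requirement.

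**The concern.** In open claims, the absence of a record may mean that the patient was well, or that care went unrecorded. If capture is poor, propensity score matching balances recorded comorbidity rather than true comorbidity, and some patients classed as new users may have had earlier steroids. To learn whether this matters, one would normally tighten the observability requirement and see whether the HR moves. SA3 relaxes it, and alters covariate measurement for everyone in the same step.

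What is at stake is interpretation. Because VIII.A cites SA3 among the ways this limitation is addressed, an SA3 HR close to the primary one could be read as evidence that missing enrollment data did no harm. The analysis cannot supply that evidence.

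**Working it through.** The protocol gives no sample size, event count or expected HR for SA3, so there is no figure to reproduce. The check is one of design logic, with illustrations on stated assumptions.

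**1. Direction of the change.** The primary criterion is at least one encounter in 183 days; SA3 asks for at least one in 365. Anyone who meets the first meets the second, so the SA3-eligible population contains the primary one. The difference is the group with an encounter only in the earlier part of the year. No poorly observed primary patient leaves, and those who enter have weaker evidence of being observable.

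**2. Feasibility.** First cohort entry is 01-April-2020 (V.C.1), and 365 days earlier is 02-April-2019. Data start on 01-December-2018 (IV), 487 days before first entry. The longer window is available for every patient, so feasibility is not the problem.

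**3. How far the SA3 HR can move.** Let f be the share of statistical information from added patients:

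log HR(SA3) = (1 − f) × log HR(primary patients) + f × log HR(added patients)

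The HR in primary patients is set at 0.80, the planning value in Table 4. The share f and the HR in added patients are assumptions, since the protocol gives neither.

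| f | added HR 0.6 | added HR 1.0 | added HR 1.25 |
|---|---|---|---|
| 5% | 0.789 | 0.809 | 0.818 |
| 10% | 0.777 | 0.818 | 0.837 |
| 20% | 0.755 | 0.837 | 0.875 |
| 30% | 0.734 | 0.855 | 0.915 |

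At small f, even a very different effect in added patients barely moves the result.

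**4. Two changes at once.** Suppose the longer covariate window also shifts the log HR in primary patients by ±0.03 (assumed), with f = 10%:

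- Added HR 1.0, shift −0.03: 0.9 × (−0.2231 − 0.03) + 0.1 × 0 = −0.2278, HR 0.796.
- Added HR 0.6, shift +0.03: 0.9 × (−0.2231 + 0.03) + 0.1 × (−0.5108) = −0.2249, HR 0.799.

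Both look like no change from 0.80, although both components moved. When the signs agree, the HR becomes 0.757 (added HR 0.6, shift −0.03) or 0.840 (added HR 1.0, shift +0.03), and nothing in the output says which change was responsible.

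**5. Why capture matters in general.** Take a comorbidity with prevalence 40% in DEX+ and 30% in referents, a death risk ratio of 2, recorded with sensitivity s and specificity 1 (all assumed). Unadjusted bias is 1.4 / 1.3 = 1.077. After matching on the recorded variable, standardised to DEX+:

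bias = 1.4 / {0.8s + (1 − 0.4s) × [1 + 0.3(1 − s) / (1 − 0.3s)]}

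This gives 1.010 at s = 0.9, 1.036 at s = 0.6 and 1.058 at s = 0.3, or 13%, 48% and 76% of the log bias. These values illustrate residual confounding from under-recording in any claims analysis, the primary one included. They do not measure an error in SA3.

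**6. The encounter window is stated in two ways.** Figure 2 (V.A) ends it at Day −1. Section V.C.3 ends it at Day 0, the admission date. Every cohort member has a hospital admission on Day 0. If that admission counts as the encounter, the exclusion removes nobody, SA3 adds nobody, and only SA3's covariate window has any effect.

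**The case against.** The best defence is that SA3 does more than produce an HR. Its comparison of 183-day and 365-day covariate status by treatment addresses differential capture directly. That stands, and a reader who inferred that SA3 has no bearing on the problem would go too far. The comparison is descriptive, however, and does not establish who was enrolled.

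Coupling the two changes also has a rationale: with a 183-day covariate window, the added patients would have little or no encounter-based covariate data. That justifies a 365-day window in the broader cohort, but not leaving out the same window in the unchanged one.

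Three stronger readings are tempting, and the documents do not support them:

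- That bundling breaks the protocol's own rule. Section V.C.3 says "The following will be evaluated (one at a time) in sensitivity analyses", but this separates the listed analyses from each other. It does not promise that each alters a single feature.
- That SA3 admits the least observable patients. Those with no encounter in 365 days stay excluded, and the added patients may simply be healthy people who use little care. Less observable is as far as the text goes.
- That new use in added patients rests on an empty washout. SA3 leaves the 90-day washout unchanged, but V.B also draws on pharmacy claims, which may exist without a medical encounter.

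The propensity score candidates include visit counts, pharmacy claims and insurance type, which partly stand in for observability, and VIII.A says its limitations will still be weighed in interpretation. Both points lower the stakes. Neither makes SA3 a test of the enrollment proxy.

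**Conclusion.** The point holds in a limited form. VIII.A cites SA3 as part of how missing enrollment information is addressed, yet SA3 loosens the proxy, changes the covariate window in the same run, and is accompanied by no analysis that tightens the proxy. Its HR cannot show whether poor observability biases the primary estimate, and it cannot assign a shift, or the lack of one, to either change.

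The size cannot be estimated from the protocol, because neither the number of added patients nor the sensitivity of capture is given. The HR range of 0.734 to 0.915 and the cancelling examples rest on assumed inputs; they show only that a stable SA3 HR is weak evidence. SA3 is one of eight supportive analyses and the primary estimate does not depend on it, so this is a worthwhile, inexpensive improvement and not a threat to the main result.

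**What to change.** 1. Split SA3. SA3a: 365-day covariate window with primary eligibility unchanged. SA3b: the broadened cohort with the 365-day window, which is the present SA3. SA3a against the primary isolates the window; SA3b against SA3a isolates the added patients.
2. Add a supportive tightening analysis restricted, in both arms, to patients with closed-claims enrollment covering Day −183 to Day 0. The protocol does not say whether enrollment spans were delivered or what share of the cohort has them. If they are unavailable, use a stricter encounter requirement, such as encounters in more than one part of the baseline period.
3. In VIII.A, cite the tightening analysis, not SA3, as the check on observability.
4. Reconcile Figure 2 (window ends Day −1) with V.C.3 (window ends Day 0), and state whether the index admission counts as the encounter.

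The cost is the extra runs and some rewording. A closed-claims subset would be smaller, with a different payer mix and a wider interval, so it should be labelled supportive only.
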